7.7.4.2 Main secondary endpoints

The main secondary efficacy endpoint will be overall survival (OS).

OS is defined as the time from diagnosis to death from any cause.

Censoring date will be the date of last contact for patients who are still alive.

7.7.4.3 Other secondary endpoints

The other secondary efficacy analyses will be the evaluation of the following outcomes:

- 1. Rate of Complete Remission (CR) CR is defined in Section 7.3.
- 2. Duration of first complete remission This is defined as the time between date of first complete remission to the date of loss of first complete remission.
- Rate of Complete Hematological Remission CHR response (Complete Hematological Remission) is defined in Section 7.3.
- 4. Rate of MRD response MRD response (Minimal residual Disease) is defined in Section 7.3.
- 5. Time to first transplantation This is defined as the time from date of diagnosis to the date of first transplantation.
- 6. Time to engraftment (neutrophil, platelet and both neutrophil/platelet) This is defined as the time from date of transplant to the date of engraftment.
- 7. Rate of engraftment failure
- 8. Rate of acute Graft versus Host disease
- 9. Rate of chronic Graft versus Host disease

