7.3.1.6 Time to transplant, time to engraftment, engraftment failure, graft versus host disease

- Time to transplant is defined from the date of diagnosis until the date of the transplant procedure.
- Time to engraftment (neutrophil, platelet and both neutrophil/platelet engraftment) is defined as the time from the date of transplant to the date of engraftment.
- Engraftment failure is defined as either definitive engraftment failure or the absence of engraftment.
- Presence/ absence of graft versus host disease; chronic or acute (Section 7.4.2.6).

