Follow-up Visit			1	2	601	777	602	778	888
Obtain Informed Consent	D	8	Х						
Patient history				-					
Inclusion/ exclusion criteria	D	7.2.2	Х						
Demography	D	7.4.2.1	Х						
Relevant medical history / current medical conditions	D			х					
Prior / Concomitant medications	D			х	Х	x			
Concomitant antineoplastic therapy	D			Х	Х	Х			
History and diagnosis of disease	D			Х					
Induction Response [Poor / Good]	D	7.4.2.2		х					
Physical examination									
General Physical Examination	S	7.4.2.7		Х	Х	Х	Х	Х	
Performance status	D	7.4.2.8		Х	Х	Х	Х	Х	
Vital Signs [Height / Weight]	D	7.4.2.9		Х	Х	Х	Х	Х	
Development & Growth [Tanner Staging]	D	7.4.2.10		х	Х	x	x	X	
Laboratory assessments	•		•	•				-	
Response status [Efficacy]	D	7.4.2.3		Х	X	X	Х	X	

Novartis Non-interventional study protocol – v02 (Clean)

Confidential

Page 25 STI571 / Glivec[®] / CSTI571I2201

			مة	_	Surveillance	Period			
	ategory	Protocol	creening .	agnosis i aseline	On Treatment Follow-Up	End of study Treatment (EOT)	Post- Treatment Follow-Up	Study Evaluation Completion	Survival follow-up
	ů	Section	ы К	Di B	Visit Dates	EOT Date	Visit Dates	EOS Date	SURV Visit
Follow-up Visit			1	2	601	777	602	778	888
Hematology	D	7.4.2.4		Х	Х	Х	Х	Х	
BM assessment / cytogenetics	D			Х	Х	Х	Х	Х	
MRD assessment	D	7.4.2.5		Х	Х	Х	Х	Х	
Extramedullary involvement [Cerebro-spinal Fluid Exam]	D			х	х	х	Х	х	
Safety									
Adverse events / Serious adverse events	D	7.3.1.8		Х	Х	х	Х	Х	
Drug administration (imatinib dosing)	D	7.4.2.11		Х	Х				
Surgery									
Transplantation and engraftment [Hematopoietic Stem Cell Treatment (HSCT)]	D	7.4.2.6			X	X	X		
End of study treatment (EOT)	D					X			
Study Evaluation Completion	D							X	
Overall Survival	D	7.3.1.2							Х

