7.4.2.6 Transplant and engraftment

- Transplant (i.e. date of transplantation, phase of transplantation, type of transplantation, source of transplantation, relationship to donor).
- Time to engraftment, engraftment failure (i.e. date, neutrophil/platelet engraftment success yes/ no, engraftment failure yes/no).
- Presence of graft versus host disease (i.e. chronic graft versus host disease presence yes/ no, acute graft versus host disease presence yes/no).

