7.7 Data analysis

All analyses will be performed by a Novartis representative and/or designee.

All data summaries and analyses will have descriptive purposes only with no formal inferential testing.

Due to the observational nature of this registry, it is expected that some specific endpoints may not be available at all time points and for the entire population. Unless otherwise specified in the Reporting Analysis Plan, the analyses will be performed on available data.

Patient efficacy, safety and tolerability outcomes of patients treated with chemotherapy + imatinib will be summarized overall, by HSCT (yes/no) and by risk group (good-risk/induction-responder) / (poor-risk/induction non-responder).

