7.7.4.1 Primary endpoint

The **primary endpoint** will be event-free survival (EFS) considering the following events: relapse at any site, development of a second malignant neoplasm or death.

Event free survival is defined as the time from diagnosis to the earliest of these events.

Censoring date will be the date of last contact for patients who did not experience any of these events.

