7.7.4.4 Methods of analysis

The efficacy endpoints will be summarized descriptively for the FAS.

Time to event endpoints (OS, EFS, transplant, engraftment) will be described using Kaplan Meier plots and associated statistics such as estimated survival rates by time points and medians along with 95% confidence intervals.

Event rates will be provided with 95% confidence intervals using Pearson-Clopper method.

On top of these analyses, analyses with a different definition of endpoint or on different subgroups will be performed:

- Analyses of OS and EFS will be performed taking into account the occurrence of transplantation procedure (by censoring at time of transplant for example). This is to avoid that prolongation in time to event after transplantation is taken as an Imatinib success.
- OS and EFS will be performed on the following subgroups:
 - subgroups based on age (with age categories selected to allow pubertal vs prepubertal differentiation),
 - subgroups based on peripheral lymphoblast count,
 - subgroups based on enrollment into approved clinical studies
 - subgroups based on type of transplant donor
- Time to transplant will be analyzed and presented according to type of transplant donor (autologous, allogeneic, syngeneic, other).

In addition, an analysis will be performed to evaluate the influence of prognostic factors (age, leukocyte count and early response, type of donor etc.) on efficacy outcome: these could include analyses of the impact of prognostic factors either on the odds of non-response to induction therapy by using logistic regression modeling or on time to event variables using cox regression modeling.

The association between MRD with other endpoints such as OS and EFS will be explored.

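### EFS by HSCT, EFS by donor type and time to first transplantation do not require the transplant to precede an EFS event, so a first transplant after relapse counts in all three

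*Protocol*

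**What the plan says.** Section 7.7 states that efficacy, safety and tolerability outcomes "will be summarized overall, by HSCT (yes/no) and by risk group". HSCT 'yes' is given no timing or remission condition.

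Time to transplant is defined twice. Section 7.3.1.6: "Time to transplant is defined from the date of diagnosis until the date of the transplant procedure". Section 7.7.4.3, for time to first transplantation: "This is defined as the time from date of diagnosis to the date of first transplantation". Neither names a disease phase. Section 7.7.4.4 describes this endpoint by Kaplan-Meier and does not mention relapse as a censoring or competing event.

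Section 7.7.4.4 also plans OS and EFS in "subgroups based on type of transplant donor", and OS and EFS analyses that take transplant into account, "by censoring at time of transplant for example".

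On the endpoint itself, relapse is one of the listed events and Section 7.7.4.1 says "Event free survival is defined as the time from diagnosis to the earliest of these events". Relapse is not among the reasons for leaving the registry (Section 7.2.5), follow-up lasts at least 5 years from the start of imatinib (Section 7.1.4), and Table 7-1 schedules transplant records on treatment, at end of treatment and in post-treatment follow-up. Section 7.4.2.6 collects "date of transplantation, phase of transplantation, type of transplantation, source of transplantation, relationship to donor".

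**The concern.** A child who relapses stays under observation. If that child then has a first transplant, it is recorded, the child falls under HSCT 'yes', and the date is an event in time to first transplantation. For EFS, the child has been put into a group by something that happened after the endpoint event. Each such child takes a failure out of 'no' and adds one to 'yes'. The donor-type subgroups inherit the same fault.

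At stake is the reading of the EFS-by-HSCT tables in an EMA-imposed study with a minimum of 50 children, where a few misplaced children move a percentage noticeably. Section 7.7.4.4 explains that its transplant-aware analyses are there to stop benefit from transplant being credited to imatinib. Removing salvaged relapses from the 'no' group works against that aim, because chemotherapy plus imatinib without HSCT then looks better than it is. Time to transplant, for its part, mixes transplants given as part of first-line treatment with those given after failure.

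**Working it through.** The protocol gives no figure to reproduce: Section 7.5 has no sample size calculation, and no transplant count or EFS by HSCT is stated. The check asks how large the artefact would be if HSCT had no effect at all.

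**Input from the protocol.** EFS of 69.6% at 48 months (Section 5.3.1, cohort 5 of the earlier trial); at least 50 children (Section 7.5); 5 years of follow-up.

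**Assumptions not in the documents.** Constant hazard; first-remission HSCT intended in 20-80%, at 0.3-0.8 years if still event-free; 80% of EFS events are relapses; 30-80% of relapsed children without an earlier HSCT are transplanted, 2-6 months after relapse; same hazard with or without HSCT.

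**Step 1, hazard.** h = -ln(0.696)/4 = 0.0906 per year. 5-year EFS = exp(-5 x 0.0906) = 63.6%, that is 31.8 of 50 event-free and 18.2 with an event.

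**Step 2, one scenario by hand (40% first-remission HSCT, 60% salvage), per 50 children.**
- First-remission HSCT done: 50 x 0.40 x exp(-0.0906 x 0.55) = 50 x 0.40 x 0.951 = 19.0. Of these, 0.40 x 31.8 = 12.7 are event-free at 5 years.
- Others: 31.0, of whom 0.60 x 31.8 = 19.1 are event-free and 11.9 have an event.
- Salvage: 11.9 x 0.8 x 0.6 = 5.7, or 5.4 once those whose transplant would fall after 5 years are removed.
- HSCT 'yes' as written: 19.0 + 5.4 = 24.4, EFS 12.7/24.4 = 52%. HSCT 'no': 50 - 24.4 = 25.6, EFS 19.1/25.6 = 75%. Difference about -23 points, with a true effect of zero.
- Transplanted by 5 years: 24.4/50 = 49% for any first transplant, against 19.0/50 = 38% before any event.

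**Step 3, range.** Simulation of the same model. 'Restricted' counts only transplants before any EFS event.

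| First-remission HSCT / salvage | Salvage per 50 (share of 'yes') | 5-year EFS yes v no, as written | Difference (points) | Difference, restricted (points) |
|---|---|---|---|---|
| 20% / 80% | 9.2 (49%) | 34.1 v 81.1 | -47 | +4.0 |
| 40% / 60% | 5.4 (22%) | 52.0 v 74.7 | -23 | +5.1 |
| 60% / 30% | 2.0 (7%) | 62.4 v 65.4 | -3 | +7.5 |
| 80% / 60% | 2.6 (6%) | 62.5 v 67.9 | -5 | +13.5 |
| 80% / 30% | 1.3 (3%) | 64.6 v 59.7 | +5 | +13.6 |

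The sign can reverse because a second bias pushes the other way: a child must stay event-free long enough to be transplanted in first remission.

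**Step 4, does restricting the flag suffice?** No. In Step 2 the restricted groups give 12.7/19.0 = 66.8% against 19.1/31.0 = 61.6%, about +5 points with no true effect. With a landmark at 0.8 years, when all first-remission transplants in this model have been done, both groups read exp(-4.2 x 0.0906) = 68.3%, and the artefact disappears.

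**Sensitivity.** With 70% of events relapses, first-remission HSCT at 3-9 months and the 48-month time point, the 40%/60% scenario gives 61% v 78%, the same pattern. Overall EFS stays at 69.6-69.7% throughout, because it does not use HSCT status.

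**The case against.** The strongest reply is that this is an open definition rather than a stated error. The protocol never says outright that post-relapse transplants count as HSCT 'yes'. Section 7.7 refers to a separate analysis plan, which is not at hand, and date and phase of transplantation are collected, which is what a timing rule needs. That stands in part: the analysis plan may settle it. But the protocol itself prescribes the yes/no split and defines time to transplant twice. Section 7.7.4.3 limits duration of remission to first remission and sets no comparable limit on transplant. Followed as written, the rule sorts EFS by a later event.

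Time from diagnosis to first transplantation is a legitimate descriptive quantity. That also stands; the difficulty is that it mixes first-line and salvage use without separating them.

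EFS censored at transplant is already safe from salvage transplants, since the EFS event comes first. True, but that analysis does not repair the yes/no table.

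A single first-remission definition applied to every analysis would do harm. It would place the toxicity of salvage transplants in the non-transplant safety table. It would also stop OS being censored at salvage transplant, against the aim stated in Section 7.7.4.4. This stands in full, and the fix is limited accordingly.

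**Conclusion.** The EFS-by-HSCT summaries, the donor-type EFS subgroups and time to first transplantation lack a condition that the transplant came before an EFS event, and this should be corrected. With no true HSCT effect, the apparent difference in 5-year EFS runs from about -47 to +5 points over 20-80% first-remission HSCT and 30-80% salvage. Both ranges are assumptions, as are the constant hazard and the 80% share of relapses among events.

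A reader might infer more than the documents support:
- That salvage transplants dominate the HSCT group. No counts are given, and the modelled share runs from 3% to 49%.
- That transplant will necessarily look harmful. The net direction depends on the unknown mix and reverses at 80% first-remission HSCT with 30% salvage.
- That the primary result is wrong. EFS on the whole full analysis set (Sections 7.7.4 and 7.7.4.1) does not use HSCT status and is unaffected.
- That a transplant before the first imatinib dose would be coded 'no' because the transplant row of Table 7-1 has no baseline mark. Section 7.4.2.6 collects the transplant date without tying it to a visit, and Section 7.1.1 allows retrospective additions, so this is at most a minor tidying point.

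All summaries are descriptive, so no test or error rate is at issue.

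**What to change.** - **EFS by HSCT and by donor type (Sections 7.7 and 7.7.4.4):** count only a first transplant performed before any EFS event, using the date and phase already collected. Make the comparison from a stated landmark or with HSCT as a time-dependent covariate, because the restricted grouping alone still favours 'yes' by about 4 to 14 points in the model above.
- **Time to first transplantation (Sections 7.3.1.6, 7.7.4.3 and 7.7.4.4):** report the cumulative incidence of first-remission transplant with relapse and death as competing events, and list post-relapse transplants separately.
- **Leave unchanged:** any-transplant status for the safety summaries and for the OS analysis that accounts for transplant.

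The cost is slightly more analysis work and a few fewer children in the HSCT group for EFS. No new data are needed.

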7.7.4.4 Methods of analysis

The efficacy endpoints will be summarized descriptively for the FAS.

Time to event endpoints (OS, EFS, transplant, engraftment) will be described using Kaplan Meier plots and associated statistics such as estimated survival rates by time points and medians along with 95% confidence intervals.

Event rates will be provided with 95% confidence intervals using Pearson-Clopper method.

On top of these analyses, analyses with a different definition of endpoint or on different subgroups will be performed:

- Analyses of OS and EFS will be performed taking into account the occurrence of transplantation procedure (by censoring at time of transplant for example). This is to avoid that prolongation in time to event after transplantation is taken as an Imatinib success.
- OS and EFS will be performed on the following subgroups:
 - subgroups based on age (with age categories selected to allow pubertal vs prepubertal differentiation),
 - subgroups based on peripheral lymphoblast count,
 - subgroups based on enrollment into approved clinical studies
 - subgroups based on type of transplant donor
- Time to transplant will be analyzed and presented according to type of transplant donor (autologous, allogeneic, syngeneic, other).

In addition, an analysis will be performed to evaluate the influence of prognostic factors (age, leukocyte count and early response, type of donor etc.) on efficacy outcome: these could include analyses of the impact of prognostic factors either on the odds of non-response to induction therapy by using logistic regression modeling or on time to event variables using cox regression modeling.

The association between MRD with other endpoints such as OS and EFS will be explored.

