7.7.4 Efficacy analyses

The efficacy analyses will be performed using the FAS.

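### Kaplan-Meier is a poor choice for time to transplant and engraftment because death competes; donor-type curves show only timing, and the overall graft rates need a transplanted denominator

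*Protocol*

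**What the plan says.** Section 7.7.4.4 of the Protocol puts four endpoints under one method: "Time to event endpoints (OS, EFS, transplant, engraftment) will be described using Kaplan Meier plots and associated statistics", with time-point estimates and medians and their 95% intervals. No competing-risk method is named.

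Censoring rules are given for two of the four. For EFS (7.7.4.1): "Censoring date will be the date of last contact for patients who did not experience any of these events". For OS (7.7.4.2): "Censoring date will be the date of last contact for patients who are still alive". Section 7.7.4.3 defines the other two without a censoring rule. Time to first transplantation: "This is defined as the time from date of diagnosis to the date of first transplantation". Time to engraftment: "This is defined as the time from date of transplant to the date of engraftment".

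Section 7.7.4.4 adds a donor split: "Time to transplant will be analyzed and presented according to type of transplant donor (autologous, allogeneic, syngeneic, other"). Section 7.4.2.6 records type, source and donor relationship as details of the transplant itself.

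On the analysis set, section 7.7.4 states: "The efficacy analyses will be performed using the FAS". Section 7.7.1 defines the FAS by receipt of imatinib plus chemotherapy, transplanted or not. The efficacy outcomes in 7.7.4.3 include engraftment failure, "Rate of acute Graft versus Host disease" and its chronic counterpart. Section 7.7 also plans every efficacy summary overall, by HSCT yes/no and by risk group, on available data unless the Reporting Analysis Plan says otherwise.

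**The concern.** A patient who dies untransplanted can no longer be transplanted, and a patient who dies or loses the graft after transplant can no longer engraft. Kaplan-Meier treats a patient censored at death as still able to have the event later, so its complement estimates a probability in a setting without deaths. That is not what a registry should report as the share of children transplanted or engrafted.

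The donor split has a different problem. Donor type exists only once the transplant has happened, so each donor group consists entirely of patients who had the event.

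The third issue is the denominator. Engraftment failure and GvHD can occur only after transplant, yet the stated analysis set includes untransplanted patients.

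Transplant, engraftment and GvHD are listed secondary objectives in Table 6-1. The registry is purely descriptive and plans a minimum of 50 patients, so the reported probabilities are its product.

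**Working it through.** The Protocol gives no figure for any of these endpoints, so there is nothing to reproduce. The sizes below are illustrations.

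**Transplant: Kaplan-Meier against cumulative incidence**

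Inputs:
- Death hazard *c*: section 5.3.1 gives 48-month OS of 83.6% in the continuous-imatinib cohort, so *c* = -ln(0.836)/4 = 0.045 per year. It is assumed that this constant rate applies before transplant.
- Transplant hazard: assumed, *l1* = 0.5 in year 1 and *l2* = 0.05 per year in years 2 to 5.

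One minus Kaplan-Meier at 5 years, deaths censored: 1 - exp(-0.5 - 4 × 0.05) = 1 - exp(-0.7) = 50.3%.

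Cumulative incidence = [l1/(l1+c)] × [1 - exp(-(l1+c))] + exp(-(l1+c)) × [l2/(l2+c)] × [1 - exp(-4(l2+c))]
- Year 1: (0.5/0.545) × (1 - exp(-0.545)) = 0.385
- Years 2 to 5: 0.580 × (0.05/0.095) × (1 - exp(-0.38)) = 0.096
- Total: 48.2% (from unrounded terms)

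The excess is 50.3 - 48.2 = 2.1 points.

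For a wider range, fix the true share transplanted *q* and the share with a competing death *d*, both assumed, with constant hazards. Then one minus Kaplan-Meier is 1 - (1-q-d)^(q/(q+d)). Excess in points:

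| q | d = 2% | 5% | 10% | 15% |
|---|---|---|---|---|
| 30% | 0.3 | 0.9 | 1.8 | 2.9 |
| 50% | 0.6 | 1.6 | 3.4 | 5.4 |
| 80% | 1.2 | 3.2 | 7.1 | 12.0 |

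**Engraftment**

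Suppose 2 of 25 transplanted patients die before engraftment and the other 23 engraft (assumed). The true proportion is 23/25 = 92%. With the two deaths censored, the last patient at risk engrafts and one minus Kaplan-Meier ends at 100%.

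**Donor-type curves**

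In one simulated cohort, 28 of 50 patients (56%) were transplanted, 21 with one donor type and 7 with another. Within each group everyone has the event, so the curves end at 21/21 and 7/7, both 100%. The overall 56% cannot be recovered from them.

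**Graft rates**

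Suppose 25 of 50 patients are transplanted and 10 of them have acute GvHD (assumed). With Clopper-Pearson intervals:
- On the FAS: 10/50 = 20.0% (10.0 to 33.7)
- Among transplanted patients: 10/25 = 40.0% (21.1 to 61.3)

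**The case against.** **Death as censoring is not written.** A reader might infer that the Protocol orders deaths to be censored. It does not: it is silent, and a Reporting Analysis Plan may settle the handling. If patients who die are kept in the risk set to the end of follow-up, Kaplan-Meier equals the cumulative incidence (56.0% in the simulated cohort, against 56.2% with deaths censored). This stands as a limit on the wording. It does not remove the point, because the Protocol itself fixes Kaplan-Meier for these endpoints, censoring is that method's default, and no rule to the contrary is stated.

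**The bias may be small.** A larger excess of 4 to 6 points follows from competing hazards of 0.09 to 0.15 per year. The lower value, though, matches the EFS rate in section 5.3.1 (-ln(0.696)/4 = 0.091), which counts relapse, and nothing in the Protocol says relapse prevents transplant. The death rate gives about 2 points. With 50 patients and a proportion near one half, the 95% half-width is about 1.96 × √(0.25/50) = 14 points. This stands for transplant. Sampling error does not excuse an avoidable bias, and for engraftment the 100% endpoint can be plainly misleading.

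**The graft denominator is largely answered.** It is tempting to conclude that the graft rates will simply be wrong. The HSCT yes/no split in section 7.7 gives the transplanted denominator, and time to engraftment starts at transplant and so cannot use the whole FAS. What remains is the overall summary, which is diluted on a literal reading, and an HSCT = no column that is 0% by construction.

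**Timing by donor type is a legitimate description.** This is correct. Calling the curves uninterpretable goes too far; they need a label.

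**Conclusion.** The point holds in a limited form. Kaplan-Meier, as named for time to transplant and engraftment, would by default overstate both probabilities. For transplant the excess is about 2 points, on assumed transplant hazards and the death rate implied by section 5.3.1, and 0.3 to 12 points over a wider assumed range. For engraftment the curve can reach 100% when some patients die first.

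That donor-type curves end at 100% follows from the text alone and needs no assumption. Dilution of the overall engraftment-failure and GvHD rates depends on reading the FAS statement literally, and the proper rate would appear in the HSCT = yes summary.

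The documents do not support saying that reported figures are wrong. None exist yet, and the handling of deaths is unstated. Primary EFS and OS are not touched. The change is worth making but is not critical.

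**What to change.** Amend section 7.7.4.4 as follows:

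- **Transplant:** replace Kaplan-Meier with Aalen-Johansen cumulative incidence in the FAS, from diagnosis, with death before transplant as the competing event.
- **Engraftment:** use cumulative incidence among transplanted patients, from transplant date, with death and graft failure as competing events.
- **Donor type:** show donor types as competing causes within the transplant analysis, or label donor-specific results as timing among transplanted patients.
- **Engraftment failure, acute and chronic GvHD:** report proportions with Clopper-Pearson intervals among transplanted patients (for GvHD, allogeneic recipients), and name that denominator.
- **GvHD over time:** use cumulative incidence only if onset dates are available. Section 7.4.2.6 lists GvHD as presence yes/no, and section 9.1 assures adverse-event monitoring only for at least 30 days (or 5 half-lives, if longer) after the last dose, so complete dates cannot be assumed.

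The cost is a change of wording and slightly more analysis work with standard software. Transplant, engraftment and death dates are already collected (7.4.2.6, 7.2.5). The main drawback is that some donor categories will be sparse in about 50 patients.

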5.2 Overview of Philadelphia positive acute lymphoblastic leukemia (Ph+ ALL)

Acute lymphoblastic leukemia (ALL) is the most common malignancy in the pediatric population (approximately 80% of childhood leukemias and 25% of all pediatric cancers), with an annual incidence rate of 1-4 new cases per 100,000, with a peak incidence at ages 2-5 years (Pui et al. 2008, Stanulla and Schrappe, 2009). Philadelphia positive acute lymphoblastic leukemia (Ph+ ALL) is characterized by the presence of the Philadelphia chromosome, a reciprocal translocation between chromosomes 9 and 22 (t(9;22)(q34;q11)) resulting in the fusion of the breakpoint cluster region (bcr) gene on chromosome 22 with c-abl gene sequences translocated from chromosome 9 and the expression of the BCR-ABL protein. Ph+ ALL accounts for up to 5% of pediatric ALL (Faderl et al. 2002).

Factors affecting the risk of ALL relapse include age, white blood cell (WBC) counts at diagnosis, presence and type of genetic abnormalities, and response to initial induction therapy. With regard to clinical factors, a poorer outcome is associated with children <1 year and >9 years of age and those with an increasing leukocyte count (Pui et al. 2006, Pui et al. 2008). Pediatric patients with B-lineage ALL are categorized as low risk, standard risk, high risk or very high risk (VHR) (Pui 2001a, Pui et al. 2001b). Pediatric Ph+ ALL is a subtype of VHR ALL, characterized by an older age (median 9-10 years vs. approximately 4-years for all pediatric ALL patients) and higher WBC counts at diagnosis. The presence of the Ph+ chromosome renders a patient very high risk ALL with a high risk of relapse and poor prognosis.

The treatment of ALL is not homogenous. Patients with high risk disease are at higher risk of relapse and receive more intensive chemotherapy than low risk patients. There is no standard chemotherapy regimen in ALL. Treatment of newly diagnosed ALL patients typically consists of several treatment phases, i.e. induction, consolidation, and maintenance. Prior to the development of imatinib, Ph+ ALL patients were treated with intensive chemotherapy followed by hematopoietic stem cell transplant (HSCT), ideally with a matched related donor, as this was shown to result in improved event-free survival (EFS) compared to either HSCT with other donors or chemotherapy alone (Arico et al. 2000).

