7.5 Study size

This is a multi-center, observational registry that is not designed to test a formal hypothesis and therefore there is no formal sample size calculation. The registry has a planned enrollment of a minimum of 50 patients.

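### The only levels written for transplant donor type pool related with unrelated allogeneic donors, although relationship to donor is already collected

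*Protocol*

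**What the plan says.** Donor type appears in three places in Protocol section 7.7.4.4.

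- **Time to transplant.** "Time to transplant will be analyzed and presented according to type of transplant donor (autologous, allogeneic, syngeneic, other"). This is the only place where levels are written out.
- **OS and EFS subgroups.** The list just above includes "subgroups based on type of transplant donor", without levels.
- **Prognostic factors.** The modelling paragraph names "prognostic factors (age, leukocyte count and early response, type of donor etc".), again without levels.

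Two other sections bear on these. In the background (5.2), HSCT before imatinib is described as "ideally with a matched related donor, as this was shown to result in improved event-free survival (EFS) compared to either HSCT with other donors"; the same sentence makes a second comparison, with chemotherapy given without transplant. In the assessments (7.4.2.6), the items recorded are "Transplant (i.e. date of transplantation, phase of transplantation, type of transplantation, source of transplantation, relationship to donor"). Type and relationship are therefore separate items, and donor matching is not among those named.

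The setting is descriptive: "All data summaries and analyses will have descriptive purposes only with no formal inferential testing" (7.7), and "therefore there is no formal sample size calculation" (7.5), with a planned minimum of 50 patients.

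**The concern.** The donor contrast for which the protocol reports an effect on EFS depends on whether the donor is related and matched. The levels written in 7.7.4.4 depend on whether the graft is autologous, allogeneic or syngeneic. The first cannot be formed from the second.

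EFS is the primary endpoint and HSCT is a major part of background treatment. In a single-arm registry with no contemporary control (7.9), the donor breakdown is one of the few planned descriptions of what transplantation may contribute to the outcome. A grouping that puts related and unrelated donors in one level spends a planned analysis of a small population without showing the distinction of interest, and it leaves unused an item that sites are already asked to record.

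**Working it through.** No formula applies. The protocol states no sample size, event count, power or alpha that depends on donor type, so there is no figure to reproduce. The check compares the sections and follows the categories through.

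**1. Where the four levels send each donor.**

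| Donor | Level in 7.7.4.4 |
|---|---|
| The patient's own cells | autologous |
| Identical twin | syngeneic |
| Non-twin related, matched | allogeneic |
| Non-twin related, not matched | allogeneic |
| Unrelated | allogeneic |

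**2. The contrast in 5.2.** It sets matched related donors against other donors. All non-twin matched related donors fall in the allogeneic level, and so do all unrelated and mismatched donors. Both sides of the contrast sit in the same cell. The only matched related donors separated out are identical twins.

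**3. What the collected items allow.** Section 7.4.2.6 lists "type of transplantation, source of transplantation, relationship to donor" as distinct items. The four levels correspond to the first. Relationship gives a related/unrelated split with no new data. It does not by itself give matched related, because matching is not listed. Related versus unrelated is therefore close to the 5.2 contrast but not the same as it.

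**4. Which analyses are affected.**

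- Time to transplant: directly, because the levels are written for it.
- OS/EFS donor subgroup: by natural reading, because the neighbouring bullet uses the same term and the protocol offers no other definition.
- Prognostic-factor models: open. The term is shorter, no levels are given, and the paragraph describes analyses that could be included.

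**5. Size.** The cell sizes would need the number transplanted and the donor mix. The protocol gives only the minimum of 50 patients overall, so no cell count or precision can be stated. The pooling shown in steps 1 and 2 does not depend on those numbers.

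**The case against.** The strongest reply is that the list governs one sentence only, on time to transplant, while the effect in 5.2 is on EFS and comes from the period before imatinib. The two statements concern different endpoints and do not contradict each other. Levels for subgroups and covariates are commonly left to the analysis plan, and 7.7 refers to one. Relationship to donor is collected, so a finer split can be produced at analysis. Transplantation is also handled elsewhere: outcomes are summarised by HSCT yes/no, and OS and EFS are analysed taking transplant into account, for example by censoring at transplant.

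Much of this stands, and it rules out several stronger readings.

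- A reader might infer that the four levels are fixed for all three uses. They are written for one; carry-over is natural but not stated.
- A reader might infer that the registry cannot show a donor effect. That is true only of the written grouping, not of the collected data.
- A reader might infer that the protocol itself names matched related donor as a prognostic factor here. Section 5.2 gives it as historical background, and 7.7.4.4 names donor type without defining it.
- A reader might extend the point to engraftment and graft-versus-host disease. Sections 7.7.4.3 and 7.7.4.4 plan no such results by donor.
- A reader might take 7.1.1 as permission to add an eCRF field for matching. It allows additions to and revisions of data already entered, which is not the same thing.

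The reply does not remove the point. The protocol did not leave donor type wholly open. It wrote one definition, and an analyst who follows it gets a less informative table than the collected data allow. The HSCT yes/no summary and the censored analyses do not describe donor type.

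**Conclusion.** The point holds in a limited form. The one written set of levels for donor type classifies the transplant rather than the donor, pools related with unrelated allogeneic donors, and cannot display a contrast close to the one cited in 5.2. It affects time to transplant as written, and the OS/EFS donor subgroup if the same definition is carried over.

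The consequence is a less informative descriptive analysis, not a wrong estimate or an inflated error rate. Any donor groups will be small, and the relevance of the 5.2 effect to patients on imatinib is not established in the protocol. The conclusion rests on two things: the ordinary meaning of the four category names, and relationship to donor being recorded as 7.4.2.6 describes. It is a near-free improvement, not an error that threatens the registry.

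**What to change.** In 7.7.4.4, replace the bracketed list with levels based on the collected relationship item:

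- allogeneic, related donor, with syngeneic donors either counted here or shown separately, and the choice stated;
- allogeneic, unrelated donor;
- autologous and other, listed only.

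State that this grouping serves time to transplant, the OS/EFS donor subgroup and the donor prognostic factor. Add that results by HLA match will be reported only where that information is available, since matching is not among the items in 7.4.2.6, and that related versus unrelated only approximates the contrast in 5.2. Source of transplantation can be tabulated alongside.

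The cost is about one sentence in the protocol, or in the analysis plan if it defines these groups, and one derivation from items already collected. It needs no new assessment and no new mandatory field. The groups should be presented as small and descriptive.
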